- ***Radiographic or other imaging assessments:*** All participants will undergo magnetic resonance imaging (MRI) evaluations at: baseline (morning prior to first TMS session) and each subsequent morning throughout the five-day TMS course (visits 3-8). MRI acquisitions will include T1-weighted structural and resting state functional magnetic resonance imaging sequences. Participants will be instructed to keep their eyes open and concentrate on a fixation cross for the duration of the resting state fMRI scan and to lie as still as possible. The fixation cross will be presented via a projector system and visualized through a mirror on the head coil. Subjects will confirm verbally during setup that the fixation cross is centered within their visual field, which can be adjusted via the head coil mirror angle. The image quality of the baseline scan will be evaluated for quality assurance, it is important that these are assessed, as they are the bases for our personalized targeting generation, as well as subsequent determination of a dose-response curve. We anticipate little to no group differences in functional connectivity between the active and sham groups at the time of baseline acquisition due to random allocation; however, this will be confirmed statistically post study completion. Following the establishment of fMRI baseline, we hypothesize that we will observe functional connectivity changes that are linearly correlated with the effects of the 5-day active TMS intervention.
- ***Administration of questionnaires or other instruments:*** The clinical active versus sham aiTBS-induced effect will be tested using either the standard (72-hour) version or a 24-hour version of the MADRS-S depending on time point (clinical improvement) and IMS-12 (acute mood state). **On the morning after the 5th day of stimulation (visit 8), participants will receive the IMS-12, MADRS-S and YMRS at the same visit as their MRI scan.**
- ***Additional optional blood draw study:***

An additional optional procedure consisting of three blood draws will be available to participants in this trial. These blood draws will occur on the In-person Screening 2/Baseline (Visit 2), the next day (Visit 8), and one-month follow up visit (Visit 9).

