9.2 SAMPLE SIZE DETERMINATION

Sample size justification (power analysis):

Key Hypothesis of the study: A significant reduction in functional connectivity between sgACC and DMN. We hypothesize that the reduction in functional connectivity between the subgenual cingulate cortex and the default mode network from baseline to after intervention day 5 will be significantly greater for participants receiving active compared to sham aiTBS. Several past studies have found no significant changes in functional connectivity with sham rTMS targeted to DLPFC^{136,212}. Using preliminary data from our open-label study of aiTBS for treatment of severe depression, there was an effect size of 1-1.47 (depending on DMN node) for change in connectivity between sgACC and DMN¹⁵⁰. One potential approach for determining the power calculation would be that considering we will have 10 unique comparisons with each day's data be compared to every other day over 5 days, and that we will be comparing across 4 DMN nodes and 2 sgACC nodes, our target alpha needs to be $0.05/(10*4*2) = 0.000625$. Thus, for an effect size of 1, alpha of 0.000625, and a power of 0.80, and powering for an independent-measures t-test, 40 participants will be required for each arm. Regarding our secondary mechanistic endpoints, we have previously found a significant correlation between change in FC between sgACC and DMN in participants receiving open-lab aiTBS, Pearson $r = 0.51$. For a point biserial model, a two-tailed 2 test, and a power target of 0.80, 25 participants will be required for each group.

Our recruitment goals are based on our primary mechanistic endpoint. Considering a ~25% attrition rate (combined participants lost to followup and unusable or missing scans), **we plan to recruit 50 participants in each arm**, as this is larger than the 18 per arm that is required to power for a significant reduction in IMS-12, and large enough to provide sufficient power for our secondary mechanistic endpoints. Given that there are ~1,000 new depressed patients at Stanford per year, >75% are TMS-naïve, there are many more than 100 patients per year that meet inclusion criteria.

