The null hypothesis (i.e. no difference in change in FC between active and sham intervention groups) will be rejected if the intervention group x time interaction has a p-value < 0.05. Data will be presented as least-squares means with standard errors.

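### Section 9.2's 80% power is not delivered on its own inputs: 50 per arm less about 25% leaves 37–38 evaluable, not the 40 required, and the calculation is not for the test that decides the primary endpoint

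*Combined protocol and SAP*

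**What the plan says.** Section 9.2 divides 0.05 by 10 × 4 × 2 to get an alpha of 0.000625. The 10 stands for "10 unique comparisons with each day's data be compared to every other day over 5 days". The 4 × 2 arises because "we will be comparing across 4 DMN nodes and 2 sgACC nodes". With an effect size of 1 and power of 0.80, the section concludes: "powering for an independent-measures t-test, 40 participants will be required for each arm". It reaches 50 per arm with the words "Considering a ~25% attrition rate (combined participants lost to followup and unusable or missing scans"), and says that the recruitment goal rests on the primary mechanistic endpoint.

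Section 8.1 places the scans at baseline, on the morning before the first session, and "each subsequent morning throughout the five-day TMS course (visits 3-8"). That is six scans, as in Section 3 and the Schedule of Activities. The hypothesis in Section 9.2 is the change from baseline to after day 5.

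Section 9.4.2 fits a linear mixed model with time and group as fixed factors and an autoregressive covariance. Its null hypothesis "will be rejected if the intervention group x time interaction has a p-value < 0.05".

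Sections 7.1 and 7.2 allow withdrawn participants to be replaced, at the team's option.

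**The concern.** The paragraph that sets the sample size has three weaknesses.

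- The attrition allowance multiplies by 1.25 where it should divide by 0.75. The assumed loss therefore takes the trial below its own required number.
- The count of comparisons fits five scans, while six are taken, and the stated hypothesis needs the first and the sixth.
- The powered procedure is a set of Bonferroni-corrected pairwise t-tests at 0.000625. The procedure that decides the primary endpoint is one interaction test at 0.05.

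At stake is whether a reader can rely on the 80%, and whether the plan gives any power for the test on which it will be judged.

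**Working it through.** **Inputs.** Section 9.2: d = 1, alpha 0.000625, power 0.80, independent-samples t-test, 40 required per arm, about 25% attrition, 50 recruited per arm. Section 9.4.1: two-tailed testing. Section 6.3: 1:1 allocation. Section 8.1: six scans.

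**1. The plan's 40.** Power = P(T > t at 1 − α/2), where T is noncentral t with 2n − 2 degrees of freedom and noncentrality d√(n/2). At d = 1 and α = 0.000625, n = 39 gives 79.5% and n = 40 gives 81.2%. The stated 40 is reproduced.

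**2. Attrition.**
- Allowance used: 40 × 1.25 = 50.
- Allowance needed: 40/(1 − 0.25) = 53.3, so 54.
- Left from 50: 50 × 0.75 = 37.5. Power is 76.0% at 37 and 77.8% at 38.
- Attrition that 50 can absorb: 50 × 0.80 = 40, so 20%.

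**3. Day-pairs.**
- Five occasions give 5 × 4/2 = 10 pairs; six give 6 × 5/2 = 15.
- With 15 pairs, α = 0.05/(15 × 4 × 2) = 0.000417.
- Required n is 42 (79.4% at 41, 81.0% at 42), and 42/0.75 = 56 to recruit.
- Power is 72.1% at 37 and 74.1% at 38.

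**4. The interaction test.** With six scans and time as a factor, group by time has 5 degrees of freedom. Its noncentrality is λ = (n/2) δ′V⁻¹δ. Here δ holds the five between-group differences in change from baseline, and V is the within-group covariance of those changes. I assumed complete data, n = 37 per arm, a difference growing linearly to d at the last scan (in SDs of the baseline-to-last change), and an F test with 5 and 5(2n − 2) = 360 degrees of freedom. The plan gives no within-subject correlation, so I varied it.

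Under compound symmetry the correlation cancels. λ = n d²[Σ(k/5)² − (Σk/5)²/6] = n d²(2.2 − 1.5) = 0.7 n d², which is 25.9 at d = 1 and 11.3 at d = 0.66.

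| Assumed covariance | Power, d = 1 | Power, d = 0.66 |
|---|---|---|
| AR(1), correlation 0.2 | 97% | 65% |
| AR(1), correlation 0.8 | 93% | 56% |
| Compound symmetry | 99% | 73% |

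For comparison, a single two-group t-test of the end-of-treatment change at α = 0.05 with 37 per arm has 99% power at d = 1 and 80% at d = 0.66.

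**The case against.** - **Replacement.** Sections 7.1 and 7.2 allow it. Full replacement to 50 evaluable per arm would give 92% at α = 0.000625 (91% at 0.000417). This stands as mitigation. But it is optional, Section 9.2 does not invoke it, and it is written for people who withdraw or are withdrawn or discontinued. It does not clearly reach a completer with an unusable scan, whom the 25% includes.
- **The rate is approximate, and 25% is not all total loss.** Both are true. At 20%, 50 is exactly enough. The mixed model can also use a participant's remaining scans. The t-test calculation behind the 40 makes no such allowance, though, and 25% is the plan's own figure.
- **Ten pairs may be intended.** The synopsis speaks of connectivity measured after each day of intervention. Five post-stimulation occasions do give 10 pairs. Section 9.2 does not say this, and its baseline-to-after-day-5 hypothesis needs the baseline scan as well. Fifteen is the more natural count from six scans, but a reader should not take it as a proven miscount. The text is ambiguous.
- **The calculation is offered only as one possible approach.** So it is, and the section never claims 80% power for the interaction. It is nevertheless the only calculation given for the primary endpoint and the source of the 40.

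**Conclusion.** The attrition error is plain. On Section 9.2's own inputs power is 76–78%, not 80%, a shortfall of 2 to 4 points. If all six scans are compared, power is 72–74%, a shortfall of 6 to 8 points. Both figures assume the full 25% loss without replacement. Separately, the plan gives no power for the interaction that decides the primary endpoint.

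Two stronger readings are tempting, and neither is supported. The first is that the primary test is underpowered or that more participants are needed. At the plan's d = 1, the interaction at 0.05 has roughly 93–99% power with 37 per arm. The second is that the primary test has 80% power at d = 0.66. That figure belongs to a single two-group end-of-treatment contrast. For a linear effect the planned interaction has about 56–73% at that size; a step-shaped effect would give 81% or more.

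The interaction figures rest on my assumptions about correlation and effect profile. The d = 1 is the plan's, taken from open-label data. This is a correction to the stated basis for the sample size, not a threat to the trial at its assumed effect.

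**What to change.** In Section 9.2:

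1. Correct the attrition step to n/(1 − 0.25), and state that 50 per arm leaves 37–38 evaluable.
2. Restate the power of the pairwise calculation as 76–78%. If all 15 pairs are intended, use α = 0.000417 and state 72–74%. Say which scans are compared. If the 80% is to rest on replacement, say so, and say whether unusable scans count.
3. Add the power of the planned group-by-time interaction at two-sided 0.05 with about 37 per arm, giving the assumed effect profile and within-subject correlation. The ranges above can serve as a guide until the team's own data supply the correlations.
4. If d = 0.66 is quoted, label it as the 80%-power effect for a single two-group end-of-treatment contrast. Making that contrast the primary test would change the analysis, which is not proposed here.

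The cost is a revised paragraph, one additional power calculation and a slightly less favourable stated power. No extra participants are needed, and the decision rule is unchanged.

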9.3 POPULATIONS FOR ANALYSES

This protocol is designed to test the mechanistic hypothesis that aiTBS reduces functional connectivity between sgACC and DMN. Thus, these mechanistic analyses will include only a Per-Protocol Analysis Dataset. The Per-Protocol Analysis Dataset defines a subset of the participants who complied with the protocol sufficiently to ensure that these data would be likely to represent the effects of study

intervention according to the underlying scientific model (e.g., participants who took at least 80% of study intervention for 80% of the days within the maintenance period).

9.4 STATISTICAL ANALYSES

9.4.1 GENERAL APPROACH

Descriptive Statistics: Categorical data will be presented as percentages. Continuous data will be presented as means with standard deviations.

Inferential tests: Statistical significance will be set at $p < 0.05$, two-tailed.

Covariates: Baseline demographic and clinical measures will be compared across intervention groups using standard statistical methods (i.e., categorical variables compared using Pearson chi square test of independence; continuous variables compared using univariate ANOVAs). Characteristics that display imbalance at the baseline measure or an association with the dependent variable will be assessed for inclusion as covariates in the final models.

Assumption checks: Continuous data will be analyzed using standard linear mixed-effects modeling in line with intent to treat analysis principles. If residuals of the standard linear models are non-normally distributed (Shapiro-Wilk), then data will be analyzed with generalized linear mixed models with Satterthwaite approximation of degrees of freedom and robust estimation of coefficients to handle violations of model assumptions. Autoregressive covariance structure will be used for all analyses except for cases in which the models fail to converge or converge on non-real solutions. In these cases, alternate covariance structures will be explored until the models converge on real solutions. All post-hoc pairwise comparisons will be Bonferroni-corrected for multiple comparisons.

General approach considerations: Primary analysis models will be reported both unadjusted and adjusted for significant clinical covariates. All statistical analysis will be conducted using SAS/STAT version 9.4 (SAS Institute Inc. 2015. SAS® 9.4 Statements: Reference, Fourth Edition. Cary, NC: SAS Institute Inc.). All statistical analyses will be overseen by our biostatistician [name], an associate professor in the Stanford department of psychiatry and behavioral sciences - Center for Interdisciplinary Brain Sciences Research. [name] holds a PhD in Applied Statistics from UCLA and is a leading expert in statistical analysis of mental health research.

9.4.2 ANALYSIS OF THE PRIMARY EFFICACY ENDPOINT(S)

Our primary hypothesis is that participants receiving per-protocol active aiTBS will demonstrate a significant attenuation of resting-state functional connectivity (FC) between subgenual anterior cingulate cortex (sgACC) and default mode network (DMN) compared to per-protocol sham intervention.

We will use fMRI to measure resting-state FC between sgACC & DMN. Participants will be treated for 5 consecutive days with 10 sessions per day of active or sham aiTBS. Participants have a baseline MRI scan prior to each day of aiTBS intervention as well as the day following the completion of intervention. After standard preprocessing of fMRI data, we will calculate FC as the correlation of the activity pattern across

time between the sgACC and DMN regions of interest. All correlation coefficients will then be transformed into Fisher's Z score for further analysis.

Baseline demographic and clinical measures will be compared across intervention groups using standard statistical methods (i.e., categorical variables compared using Pearson chi square test of independence; continuous variables compared using univariate ANOVAs). Characteristics that display imbalance at the baseline measure or association with the dependent variable will be assessed for inclusion as covariates in the final models. Differences in effects as a function of gender will be considered for all analyses.

FC data being a continuous variable, will be analyzed using standard linear mixed-effects modeling, with time and intervention group (active vs. sham) set as fixed factors. Time (throughout the intervention) will be set as the within-subject, repeated measure. The effects of intervention group, time, and their interaction will be included in the model. If residuals of the standard linear models are non-normally distributed (Shapiro-Wilk), then data will be analyzed with generalized linear mixed models with Satterthwaite approximation of degrees of freedom and robust estimation of coefficients to handle violations of model assumptions. Autoregressive covariance structure will be used unless the model fails to converge or displays variance inflation. In these cases, alternate covariance structures will be explored until the models converge on real solutions. All post-hoc pairwise comparisons will be corrected for multiple comparisons.

The null hypothesis (i.e. no difference in change in FC between active and sham intervention groups) will be rejected if the intervention group x time interaction has a p-value < 0.05. Data will be presented as least-squares means with standard errors.

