3 OBJECTIVES AND ENDPOINTS

OBJECTIVES	ENDPOINTS	JUSTIFICATION FOR ENDPOINTS
Primary		
To establish a resting state functional connectivity (RS FC) dose-response curve of active versus sham aiTBS.	Change in RS FC between the sgACC and DMN over 5-days of active aiTBS as compared to sham aiTBS. RS FC will be measured on the morning of each intervention day and the day following intervention.	We hypothesize that participants (n=50) receiving active aiTBS applied to DLPFC-sgACC will demonstrate a significant attenuation of RS FC between sgACC and DMN compared to sham (n=50) after each day of stimulation and these effects will accumulate linearly over the course of the 5 days of aiTBS. The central, consistent change in neurocircuitry observed in depression is hyperconnectivity between the SCC and DMN ⁴³ and our preliminary data involving RS FC changes from aiTBS demonstrates highly significant changes ¹⁹⁴ .
Secondary		

(a) To determine the relationship between active versus sham aiTBS-induced clinical improvement (as measured by reduction of the MADRS-S) and changes in RS FC between the sgACC and DMN.
 
(b) To determine the relationship between acute mood state (as measured by the IMS-12) and changes in RS FC between the sgACC and DMN in those receiving active versus sham aiTBS.
	
(a) Relationship between clinical improvement (measured by the MADRS-S) and RS FC between the sgACC and DMN.
 
MADRS-S will be collected at baseline, the end of each intervention day, the day following intervention, and 1-month after intervention. RS FC will be measured on the morning of each intervention day and the day following intervention.
 
(b) Relationship between acute mood state (measured by the IMS-12) and RS FC between the sgACC and DMN.
 
IMS-12 will be collected at baseline, on the morning of each intervention day, and the day following intervention. RS FC will
	Our mechanistic hypothesis is that active versus sham aiTBS-induced improvement in mood will be linear, related to session number (accumulated pulse dose), and will be associated with (accumulated) decrease in sgACC- DMN resting state functional connectivity, as compared to sham.

	be measured on the morning of each intervention day and the day following intervention.	
Exploratory		

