4 STUDY DESIGN

4.1 OVERALL DESIGN

Hypothesis: Participants (n=50) receiving active aiTBS applied to DLPFC-sgACC will demonstrate a significant attenuation of RS FC between sgACC and DMN compared to sham (n=50) after each day of stimulation and these effects will accumulate linearly over the course of the 5 days of aiTBS.

Phase: This is a mechanistic study similar to a phase 2 trial.

Trial Design: Randomized, sham-controlled, double-blinded mechanistic study.

Methods to Minimize Bias: This study will achieve robust and unbiased results via several design features including: explicit inclusion/exclusion criteria; randomization of intervention condition; the use of a validated sham control; blinding; use of validated laboratory and interview/self-report measures and methods; explicit hypotheses and corresponding planned statistical analyses; power estimates; planned handling of retention/attrition and missing data; and, careful consideration of potential confounds. All experimental details will be reported in a fully transparent manner to support replication.

Dose Escalation: TMS stimulation dose will be individually determined according to 90% rMT plus depth correction, and then the aiTBS protocol will be administered with a consistent dose across all participants receiving active stimulation of 18,000 pulses/day and 90,000 pulses/course.

The goal of treatment in this study is to ensure the correct amount of treatment (90% of motor threshold) is received in the target location (L-DLPFC) rather than under-stimulating and under- treating participants. Depth correction accounts for the variable distances between the scalp and motor hotspot and scalp and treatment target from person to person. In other words, this is a personalized treatment intensity that takes into account individual variability. However, to ensure safety we never treat higher than 120% of the person's resting motor threshold, which is the standard TMS treatment intensity in routine clinical practice.

Study Arms: Two arms, active vs sham in 50:50 randomization

Site(s): Single Site (Department of Psychiatry & Behavioral Sciences, Stanford University)

Name of Study Intervention: Accelerated intermittent theta-burst stimulation (aiTBS).

Interim Analysis: N/A

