9 STATISTICAL CONSIDERATIONS

9.1 STATISTICAL HYPOTHESES

- Primary Mechanistic Endpoint:

We hypothesize that the reduction in resting-state functional connectivity between the subgenual anterior cingulate cortex and the default mode network from baseline through intervention day 5 will be significantly greater for participants receiving active as compared to sham aiTBS.

- Secondary Mechanistic Endpoints:
 - (a) We hypothesize that there will be a significantly greater association between the change in depression symptoms (as measured by the MADRS-S) and the change in resting-state functional connectivity between the subgenual anterior cingulate cortex and the default mode network from baseline to after intervention day 5 for participants receiving active as compared to sham aiTBS.
 - (b) We hypothesize that there will be a significantly greater association between acute mood state (as measured by the IMS-12) and the change in resting-state functional connectivity between the subgenual anterior cingulate cortex and the default mode network from baseline to after intervention day 5 for participants receiving active as compared to sham aiTBS.

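### The primary success rule is an omnibus group-by-time test that requires no direction, day-5 difference or linear trend, so meeting it does not establish the stated hypotheses; the connectivity outcome is also not reduced to one value

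*Combined protocol and SAP*

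**What the plan says.** The decision rule is in Section 9.4.2 of the combined protocol and SAP: the null of no difference in change in connectivity "will be rejected if the intervention group x time interaction has a p-value < 0.05". The model is a linear mixed model "with time and intervention group (active vs. sham) set as fixed factors", plus their interaction. Section 9.4.1 sets the level: "Statistical significance will be set at $p < 0.05$, two-tailed".

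Section 3 gives the scan schedule: "RS FC will be measured on the morning of each intervention day and the day following intervention". That is six scans, Visits 3 to 8.

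Two hypotheses are attached to this outcome. Section 9.1 predicts that the reduction "from baseline through intervention day 5 will be significantly greater for participants receiving active as compared to sham aiTBS". Section 4.1 predicts separation from sham after each day and that "these effects will accumulate linearly over the course of the 5 days of aiTBS". Sections 1.1 and 3 make the dose-response curve the primary objective.

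On the outcome itself, Section 9.4.2 says only that connectivity is a correlation between the sgACC and DMN regions of interest, and that "All correlation coefficients will then be transformed into Fisher's Z score for further analysis". Section 9.2 says "we will be comparing across 4 DMN nodes and 2 sgACC nodes". The only multiplicity control in Sections 9.4.1 and 9.4.2 is for post-hoc pairwise comparisons.

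**The concern.** The rule and the hypotheses ask different questions. The interaction asks whether the two profiles differ in any way. The hypotheses ask whether active lowers connectivity more than sham by day 5, and whether the gap widens in a straight line. A p-value below 0.05 answers the first question only.

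Off-hypothesis profiles are not far-fetched here. The background (Section 2.1) cites ECT data in which an early fall in connectivity predicted a later rise. It also reports that, in the group's own earlier data, the participants with the smallest falls improved most. If such a profile occurred, the trial would meet its success rule without the hypothesised effect. Choosing which day or direction to stress would then happen after the data were seen.

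A separate gap is that several coefficients exist per scan and no rule says which one, or which average, enters the model.

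**Working it through.** **1. The plan's own figure.** Section 9.2 uses alpha = 0.05/(10 × 4 × 2) = 0.000625, an effect size of 1, power 0.80 and an independent two-sample t-test. The noncentral t gives 39.3, so 40 per arm (power 0.811 at 40). The stated 40 reproduces. That sized test is a t-test at 0.000625; the planned test is an interaction at 0.05.

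**2. Degrees of freedom.** Six scan times as a factor and two groups give (6 − 1) × (2 − 1) = 5 df. The documents do not state this number; it follows from time being a fixed factor.

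**3. Method.** Let δ be the active-minus-sham difference at each scan, in SDs of the change from Visit 3 to Visit 8. For the omnibus test the noncentrality is λ = Δ′V⁻¹Δ, where Δ holds the five differences from baseline and V is their covariance. Power comes from the noncentral F with 5 and 2n − 2 df. The 1-df contrasts use 1 and 2n − 2 df. Scan correlations are assumptions. The sample is 40 per arm (the plan's requirement) or 37 (50 × 0.75 = 37.5).

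**4. A transient difference, zero at Visit 8.** Take a 0.6 difference on the two middle scans and zero elsewhere, with n = 40. Under equal correlation λ = n × Σ(δ − mean)². The mean is 0.2, so the sum is 2 × 0.4² + 4 × 0.2² = 0.48 and λ = 40 × 0.48 = 19.2. The omnibus test rejects with probability 0.92. Under AR(1) with correlation 0.3 to 0.7 it is higher still. The Visit 3 to Visit 8 contrast rejects at its nominal 0.05.

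**5. A rise on active.** λ is quadratic in δ, so changing the sign changes nothing. For a linear separation reaching 0.6 at Visit 8, AR(1) 0.5 and n = 40, λ = 7.44. Power is about 0.50 whether connectivity falls or rises (0.52 if the denominator df is taken as 5 × 78 = 390).

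**6. Power if the hypothesis is true.** Linear accumulation, AR(1) 0.3 to 0.7, 37 to 40 per arm:

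| Effect at Visit 8 | Omnibus, 5 df | Visit 3–8 contrast, 1 df | Linear trend, 1 df |
|---|---|---|---|
| 0.5 (assumed) | 31–38% | 56–60% | 54–63% |
| 1 (Section 9.2) | 91–96% | about 99% | 98% or more |

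With equal correlation at 0.5 the figures are 43–47%, 56–60% and 71–74%. The plan names an autoregressive structure first, so the table is the closer guide.

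**7. Node pairs.** 4 × 2 = 8. If all eight were tested at 0.05 and any one counted as success, familywise error would be 1 − 0.95⁸ = 0.337 for independent tests. By simulation of 1-df tests it is about 0.25 at between-test correlation 0.5 and 0.19 at 0.7. For 5-df tests the corresponding figures are about 0.26 and 0.20.

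**The case against.** The interaction does test the null as Section 9.4.2 words it. Least-squares means will be reported and post-hoc pairwise comparisons corrected, so a rise on active or a mid-week blip would be visible. This stands, and it limits the point to the success rule: those follow-ups are not part of it. Two-sided testing is ordinary and is not the complaint; the proposed contrast is two-sided too.

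A reader might infer that eight node pairs will be tested uncorrected. The documents do not support that. Section 9.4.2 never says eight models will be run, the endpoint is worded as a single sgACC-DMN connectivity, and Section 2.1 reports the earlier result first as a mean. The 4 × 2 count appears only in the sample-size section, as one possible approach. What stands is that the reduction to one outcome is unspecified.

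A reader might also infer that the trial is underpowered because of the omnibus test. At the plan's own effect size it is not. The effect of 0.5 is this review's assumption, and the large advantage of the linear trend over the Visit 3–8 contrast appears only under equal correlation.

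Finally, because the primary objective is a dose-response curve, a case exists for making the linear trend primary. The order proposed below follows Section 9.1; either order repairs the rule if it is fixed in advance.

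**Conclusion.** The concern holds for the success rule. As written, p < 0.05 on the interaction would not by itself show that active aiTBS lowers sgACC-DMN connectivity more than sham by day 5, or that the effect accumulates linearly. Linearity of this outcome is tested nowhere in Sections 9.4.1 to 9.4.3. The illustration of size is a probability above 0.9 of declaring success on a transient difference that is zero at Visit 8. It rests on the 5-df reading, 40 per arm, a difference of 0.6 SD of change on two scans, and the assumed correlations.

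The unspecified outcome is a second, smaller gap. The 19–34% familywise error is conditional on testing all eight pairs and accepting any one. Lost power is secondary to what a rejection means.

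**What to change.** Amend Section 9.4.2 before unblinding:

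- **Outcome.** Prespecify one connectivity summary, for example the mean Fisher-z over the sgACC-DMN node pairs, or state a correction across the pairs.
- **Primary test.** The 1-df active-minus-sham contrast of change from Visit 3 to Visit 8, from the same mixed model, two-sided 0.05. It supports the hypothesis only if the estimate is negative.
- **Second, in fixed order.** The 1-df group-by-linear-day contrast, reported with the 4-df lack-of-fit test.
- **Descriptive.** The omnibus interaction.

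The cost is wording; model, scans and sample are unchanged. There are two real downsides. The contrast is less sensitive to an effect that peaks mid-week and disappears, which is not the stated hypothesis. Averaging may dilute an effect that differs by node: Section 2.1 reports significant falls for 3 of 4 DMN nodes, and Section 9.2 gives effect sizes from 1 to 1.47 depending on node. If that matters, the corrected per-pair option is the alternative.
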